3.7 Statistical Considerations

3.7.1 Sample size calculation

The total minimum sample size required is **N=1000** (500 in each intervention arm) in order to have 90% statistical power to detect a rate ratio (RR) of 0.50 in the time to progression to requiring hospitalization or death, assuming a standard-of-care rate of progression of 12%. We also assumed an accrual time of 3-6 months and make allowance for cumulative loss to follow-up of 3% per arm although we expect this will be lower (i.e., <1%).

3.7.2 Statistical analysis methods

The primary hypothesis of efficacy will be conducted under the intention-to-treat principle; all randomized participants will be included in the analyses. All results will be analyzed with 2-sided level of significance of 0.05.

Given the fixed 45 day time period of assessment of the primary outcomes of progression, we will compare the proportions of progression events between the two study arms rather than the times to progression. The primary analysis will use the Z-test for comparison of proportions. We will also secondarily adjust the intervention effect for demographics, and exposure characteristics of participants, using logistic regression models.

Descriptively, Kaplan-Meier curves of the estimated time to hospitalization will be constructed. This secondary analysis will use the Log-rank statistic, stratified by center. Secondary analyses will include adjusting the intervention effect for demographic and exposure characteristics of the participants using Cox proportional hazards regression models.

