3.5 Study Outcomes

3.5.1 Primary efficacy outcome

The primary outcome is admission to hospital or mortality.

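### Section 3.7.2 names hospitalization alone as the endpoint of the outpatient time-to-event analysis, while the primary outcome and the sample size use hospitalization or death

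*Protocol*

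**What the plan says.** Protocol section 3.5.1 defines the outpatient primary outcome: "The primary outcome is admission to hospital or mortality". Section 3.7.1 sizes the trial on a rate ratio of 0.50 "in the time to progression to requiring hospitalization or death". Both include death.

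Section 3.7.2 makes the primary analysis a Z-test on the proportions with a progression event in the fixed 45-day window, with logistic regression as its adjusted version. It then turns to time-to-event methods: "Descriptively, Kaplan-Meier curves of the estimated time to hospitalization will be constructed". The next sentence gives the test: "This secondary analysis will use the Log-rank statistic, stratified by center". A further sentence adds Cox models adjusted for demographic and exposure characteristics, without saying which event they model. The section does not say how a death before admission is handled and names no competing-risk method.

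Section 3.5.2 lists mortality and hospital admission as separate secondary outcomes.

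**The concern.** Sections 3.7.1 and 3.7.2 are consecutive and describe different time-to-event endpoints. The first has hospitalization or death; the second has hospitalization only. This is an endpoint that the protocol states, and a SAP written to follow it would carry the mismatch forward.

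Participants are at home when enrolled, so a death without prior admission is possible. In a standard Kaplan-Meier, log-rank or Cox analysis of time to hospitalization, such a participant leaves the risk set at death as if admission could still have followed. This has two consequences. The Kaplan-Meier complement no longer estimates the proportion admitted. The between-arm comparison also becomes blind to an exchange of admissions for deaths, which the composite outcome is built to count. A reader shown these curves beside the primary result may take them as its picture over time, which they are not.

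**Working it through.** **1. The plan's own figure, to see which endpoint it is built on.** Inputs from section 3.7.1: control risk 12%, ratio 0.50, power 90%, loss 3% per arm. From 3.7.2: two-sided 0.05.

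- Two proportions, 12% against 6%, pooled variance under the null: n = [1.960 × √(2 × 0.09 × 0.91) + 1.2816 × √(0.12 × 0.88 + 0.06 × 0.94)]² / 0.06² = 476.01, rounded up to 477 per arm, 954 in total. Allowing for loss, 954 / 0.97 = 984.
- Schoenfeld events: 4 × (1.960 + 1.2816)² / (ln 0.5)² = 87.5, rounded up to 88. The active risk is 1 − 0.88^0.5 = 6.19% and the mean risk 9.10%, so N = 88 / 0.0910 = 967. Allowing for loss, 967 / 0.97 = 997.

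Both agree with the stated 1000. The sizing already rests on hospitalization or death, so aligning 3.7.2 with it does not change N.

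**2. What the hospitalization-only endpoint does if deaths replace admissions.** The protocol gives no rate of death before admission, so the splits below are assumed. Let h be the proportion admitted by day 45 and d the proportion dying without admission, with constant hazards and censoring at death. The total cumulative hazard is H = −ln(1 − h − d), and the admission part is H × h / (h + d). With h + d = 12% in both arms, H = −ln 0.88 = 0.1278 in both. The composite hazard ratio is therefore 1.00, and the admission hazard ratio reduces to h(active) / h(control). Its approximate standard error on the log scale, at 500 per arm, is √(1/(500 h₀) + 1/(500 h₁)).

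| Control h, d | Active h, d | Hospitalization HR | p | Composite HR |
|---|---|---|---|---|
| 11.5%, 0.5% | 10%, 2% | 10/11.5 = 0.870 | 0.47 | 1.00 |
| 11%, 1% | 9%, 3% | 9/11 = 0.818 | 0.32 | 1.00 |
| 12%, 0% | 9%, 3% | 9/12 = 0.750 | 0.14 | 1.00 |
| 12%, 0% | 8%, 4% | 8/12 = 0.667 | 0.047 | 1.00 |
| 11%, 1% | 7%, 5% | 7/11 = 0.636 | 0.037 | 1.00 |

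A nominally significant false benefit needs a swap of about 4 percentage points. That is 0.04 × 500 = 20 extra deaths before admission in the active arm.

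**3. Whether the swap would show elsewhere.** In the first two rows, a Z-test on the assumed deaths alone (0.5% v 2%; 1% v 3%, i.e. 5 v 15) gives p of about 0.03 and 0.02. Fisher's test for 5 v 15 gives 0.04. Deaths after admission are left out here and would add to both arms.

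**4. Size of the Kaplan-Meier overstatement.** The complement is 1 − exp(−H × h/(h + d)). For h = 11%, d = 1% it is 11.06%, against 11.0% truly admitted. For h = 9%, d = 3% it is 9.14%, against 9.0%.

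**5. Two cases with no false benefit.**

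- Deaths halve along with admissions (11%, 1% v 5.5%, 0.5%): both hazard ratios are ln 0.94 / ln 0.88 = 0.484.
- Deaths are added while the admission hazard is unchanged (from 11%, 1% with the death hazard tripled): the hospitalization hazard ratio stays at 1.00 and the composite rises to (11 + 3)/12 = 1.17. The hospitalization analysis misses this harm but does not show benefit.

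**The case against.** The strongest reply is that little depends on this analysis. The section calls the curves descriptive and compares proportions in preference to times. The primary Z-test counts every death, mortality is its own secondary outcome, malignant arrhythmia is a defined safety outcome, and an independent committee monitors the data. Hospital admission is also a prespecified secondary outcome, so a time-to-hospitalization analysis is legitimate in itself. Censoring at death then gives an ordinary cause-specific comparison. All of this stands, and it is why the point is minor. It does not remove the mismatch. The log-rank test is labelled a secondary analysis, and section 3.7.2 states: "All results will be analyzed with 2-sided level of significance of 0.05". The result is therefore tested, and the section offers no time-to-event analysis of the outcome on which 3.7.1 sizes the trial.

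A reader might infer more than the text supports:

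- That the protocol rules deaths before admission to be censored. It states no rule. Censoring is the default of the named methods, and a SAP could set something else.
- That the Cox model is fixed on hospitalization. Its sentence names no endpoint; only its position after the log-rank sentence suggests one. The primary result already has an adjusted version, the logistic model.
- That a death at home can only lower the apparent hospitalization rate. Leaving the risk set does not by itself lower the hazard. Step 5 shows that apparent benefit needs deaths to replace admissions.
- That the trial could wrongly conclude benefit. Its efficacy conclusion rests on the composite, which counts these deaths.

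**Conclusion.** The point holds as a minor inconsistency. Section 3.7.2 names hospitalization alone for the outpatient Kaplan-Meier and log-rank analysis, and by context for the Cox model, while 3.5.1 and 3.7.1 use hospitalization or death. That mismatch is plain in the text and does not depend on any assumed rate.

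The numerical consequence does depend on assumptions: constant hazards, censoring at death, and a split between admissions and deaths that the protocol does not give. Under the modest splits examined, a null composite would appear as a hospitalization hazard ratio of 0.87 or 0.82, far from significance at 500 per arm. The Kaplan-Meier overstatement is at most 0.14 percentage points in those cases. The primary conclusion and the sample size are not affected.

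**What to change.** In section 3.7.2, define the endpoint of the Kaplan-Meier curves, the log-rank test and the Cox model as time from randomization to the first of hospital admission or death, censored at day 45 or last contact if earlier. Name it for the Cox model explicitly.

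If a curve for admission alone is also wanted, present it as a cumulative incidence function with death before admission as a competing event, beside the mortality result.

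The cost is one or two sentences. No new data are needed, because dates of admission and death are required for any of these curves, and N stays at 1000.

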3.7.3 Planned subgroup analyses

We will explore whether the following variables modify treatment effect: age and sex and the presence or absence of comorbidities.

4. Inpatient trial: Preventing disease progression in COVID positive inpatients

4.1 Study Objectives

4.1.1 Primary objectives

To evaluate if AZCT compared to usual care results in reduced requirement for invasive mechanical ventilation or mortality for hospitalized patients diagnosed with COVID-19.

4.1.2 Secondary efficacy objectives

To evaluate if AZCT compared to usual care results in reductions in mortality, invasive mechanical ventilation, admission to intensive care unit, renal replacement therapy, and extracorporeal support in outpatients and inpatients diagnosed with COVID-19.

4.1.3 Tertiary efficacy objectives

To evaluate if AZCT compared to usual care results in reductions in length of ICU stay, length of hospital stay, non-invasive ventilation, and duration of ventilation.

4.1.4 Translational objectives

To evaluate if AZCT compared to usual care results in reductions of viral titre and inflammatory markers and to assess whether expression of the ACE-2 receptor is associated with mortality.

4.1.5 Safety objectives

To evaluate the whether the risk of the following is increased in patients receiving COVID-19 compared with those receiving usual care: malignant arrhythmia requiring intervention, agranulocytosis, Stevens-Johnson syndrome/toxic epidermal necrolysis, and retinal toxicity.

4.2 Study Design

4.2.1 Type of study

A multi-centre, open-label, parallel group, randomized controlled trial evaluating the efficacy and safety of the AZCT compared to usual care in inpatients with COVID-19.

4.2.2 Expected number of patients

The minimum sample size for the study is a minimum of 530 patients. However, this sample size may change as this trial has an adaptive design.

4.2.3 Allocation procedure

Randomization: Eligible patients that have provided informed consent will be randomized via the central IWRS at the Population Health Research Institute. Each patient will be assigned to one of two groups, AZCT plus usual care or usual care, in randomly permuted blocks (undisclosed sizes to maintain concealment of allocation). The allocation will be communicated to site personnel and patients will be made aware of their assignment. It is not practical to use placebo. It would likely entail considerable delays in starting the trial but the outcomes are likely to occur and be ascertained independent of the knowledge of the treatment allocation. Therefore, the results are likely to be unbiased.

Stratification: randomization will be stratified by site.

4.2.4 Duration of the study period for each subject

Patients will be followed for 45 days from the time of randomization. Data of events occurring during hospital will be obtained from hospital records supplemented by a telephone call or follow up at 7-10 days and at 45 days after randomization. Participants will receive a telephone call at 12 months to determine vital status.

4.3 Study population

These patients are admitted (or waiting for admission) to the hospital for COVID-19 at the time of enrolment.

4.3.1 Inclusion criteria

- 1) Age ≥ 18 years of age
- 2) Informed consent
- 3) Diagnosis of active COVID-19 confirmed by established testing

4.3.2 Exclusion criteria

- 1) G6PD deficiency
- 2) Contra-indication to chloroquine or azithromycin
- 3) Already receiving chloroquine or azithromycin

4.3.3 Adaptive design features

Adaptive intervention arms: The DSMC and the Steering Committee will keep abreast of other ongoing trials and if other promising interventions emerge, may recommend adding (or replacing) one arm with the new promising intervention. They will assess the results of the translational objectives when available and may add a chloroquine loading dose if a large reduction in viral titres is not observed with the current regimen.

Adaptive sample size: Sample size calculations are based on disease progression rates that are not well known. We remain flexible, and the DSMC will be monitoring the possibility that the assumptions for sample size calculations may be modified with emerging information from this trial or other ongoing trials. If recruitment is going well, the steering committee may decide to extend recruitment as long as the independent DSMC does not terminate the trial for clear evidence of efficacy, futility (low probability) to detect a clinically meaningful difference (e.g. a 20% RRR in events) or concerns about safety.

Note, the DSMC will review the data from the two trials to make its decisions.

4.4 Study Procedures

In order to make it possible to implement this protocol where resources are scarce, we have simplified trial procedures, and data collection. Direct electronic data entry is encouraged.

4.4.1 Consenting process

All patients capable of consenting will provide informed consent. If the patient is deemed incapable of consenting, their substitute decision maker will be contacted. We will explain the trial, answer their questions and, document the consent process.

4.4.2 Interventions

Blinding: Patients and healthcare providers will not be blinded to treatment. To account for this, we have objective outcome definitions to minimize the opportunity for bias to influence event assessment.

Consenting participants will be randomized to receive AZCT plus usual care or usual care.

AZCT Arm

Chloroquine

Adults with a bodyweight \geq 50 kg: 500 mg twice daily for 7 days Adults with a bodyweight < 50 kg: 500 mg twice daily on days 1 and 2, followed by 500 mg once daily for days 3-7.

Azithromycin

500 mg on day 1 followed by 250 mg daily for 4 days

Usual Care

We will place no constraints for treating physicians on the therapies with respect to usual care. We will document information on all key co-interventions, including information on drugs at the time of randomization and post randomization /during hospitalization.

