Preventing people infected with COVID-19 from developing severe enough symptoms to require hospitalization is as important as treating people with COVID-19 pneumonia from deteriorating and needing ventilation or experiencing death. Therefore, we have established a program that includes two parallel trials; an **outpatient trial** seeking to prevent hospital admission and mortality, and an **inpatient trial** seeking to prevent need for mechanical ventilation or mortality. This program is a priority. If this therapy is proven conclusively to be effective, it will be used around the world. If it proves ineffective, other treatments will be explored emergently using the platform we (and other investigators) will establish.

As we design the trials, we acknowledge that many of the details usually available to design a study are not reliably available. This includes event rates (although we have made the best estimate using available data), potential size of the study or the numbers of cases that can be enrolled within a reasonable period as the number of cases is expected to increase rapidly in Canada and in many other countries). We have therefore designed these trials using the best available data, our judgement and with the goal of recruiting as many patients as possible (but at least 1000 into an outpatient trial and at least 530 into the inpatient trial). We have also built in two key mechanistic substudies testing the effects of the regimen on viral loads and on inflammation – to get an early indication of potential efficacy. During the conduct of the trials, we may need to make adjustments to several aspects of study design. To enable this and to monitor safety, the trial data will be reviewed periodically by an expert and independent data and safety monitoring committee (DSMC). We may also consider adding new arms or replacing existing arms (if they are shown to be ineffective based on emerging data) as promising new treatments emerge.

2. Program Hypothesis

Azithromycin in combination with chloroquine therapy (AZCT) on top of usual care will reduce disease progression of COVID-19 compared to usual care.

3. Outpatient trial: Preventing disease progression in COVID positive outpatients

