3.3.2 Exclusion criteria

- 1) Known glucose-6-phosphate dehydrogenase (G6PD) deficiency
- 2) Contra-indication to chloroquine or azithromycin
- 3) Already receiving chloroquine or azithromycin

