3.4.2 Interventions

Blinding: Patients and healthcare providers will not be blinded to treatment. To account for this, we have objective outcome definitions to minimize the opportunity for bias to influence event assessment.

Consenting participants will be randomized to receive AZCT plus usual care or usual care.

AZCT Arm

Chloroquine

Adults with a bodyweight ≥ 50 kg: 500 mg twice daily for 7 days Adults with a bodyweight < 50 kg: 500 mg twice daily on days 1 and 2, followed by 500 mg once daily for days 3-7.

Azithromycin

500 mg on day 1 followed by 250 mg daily for 4 days

Usual Care

We will place no constraints for treating physicians with respect to usual care. We will document information on all key co-interventions, including information on drugs at the time of randomization and post randomization/during hospitalization.

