4.6.2 Statistical analysis methods

The primary analysis of efficacy will be conducted under the intention-to-treat principle; all randomized participants will be included in the analyses. All results will be analyzed with 2-sided level of significance of 0.05. Given the rapid assessment of the primary outcomes of progression, and the expected absence of loss to follow-up, we will compare the proportions of progression events between the two study arms rather than the times to progressions. The primary analysis will use the Z-test for comparison of proportions. Secondary analyses will include adjusting the intervention effect for demographics, exposure characteristics, and severity of disease upon admission, using logistic regression models.

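### Usual care is unrestricted after open-label randomization, so controls may be given the study drugs for COVID-19 and the intention-to-treat contrast may be diluted

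*Protocol*

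**What the plan says.** The hypothesis in Protocol section 2 is "Azithromycin in combination with chloroquine therapy (AZCT) on top of usual care will reduce disease progression of COVID-19 compared to usual care". The control arm is meant to show what happens without AZCT.

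Section 3.4.2 (outpatients) sets the content of that arm: "We will place no constraints for treating physicians with respect to usual care". Section 4.4.2 (inpatients) does likewise: "We will place no constraints for treating physicians on the therapies with respect to usual care". Both sections add that key co-interventions, including drugs started after randomization, will be recorded.

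The study drugs are restricted only by the third exclusion criterion in 3.3.2, repeated in 4.3.2: "Already receiving chloroquine or azithromycin". This applies at entry. Section 1 states that the word chloroquine covers hydroxychloroquine as well.

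Allocation is open to patients and providers. Both primary analyses follow intention-to-treat: "The primary hypothesis of efficacy will be conducted under the intention-to-treat principle" (3.7.2) and "The primary analysis of efficacy will be conducted under the intention-to-treat principle" (4.6.2).

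**The concern.** Because the protocol sets no limit on usual care and has no rule on the study drugs after entry, a physician can follow it exactly and still give a control patient part or all of the tested regimen for COVID-19. The comparison then drifts from AZCT versus no AZCT towards AZCT versus some AZCT.

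Under intention-to-treat this attenuates a true benefit and a true harm alike. A null result becomes harder to read, because it could mean an inactive regimen or a treated control arm. The futility judgement in 3.3.3 and 4.3.3, which uses a 20% relative risk reduction (RRR) as its example, would rest on the same attenuated contrast.

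Only use before the primary event matters. For outpatients "The primary outcome is admission to hospital or mortality", so drugs started after admission cannot change it. For inpatients not intubated (or about to be) at randomization, drugs started after intubation come after the primary event.

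**Working it through.** **Inputs from the Protocol**

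- Inpatient (4.6.1): control risk 30%, RRR 40%, 265 per arm, power 90%, loss to follow-up below 1%.
- Outpatient (Synopsis and 3.7.1): control risk 12%, RRR 50%, 500 per arm, power 90%. The plan will "make allowance for cumulative loss to follow-up of 3% per arm although we expect this will be lower", so I use 500 × 0.97 = 485 evaluable per arm.
- Both: Z-test for two proportions, two-sided 0.05.

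**Inputs assumed, because the Protocol gives none**

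- *c*, the share of controls given the study drugs before the event: 5% to 30%.
- *f*, the share of the effect they receive: 1 (worst case) or 0.5 (one drug only, or late use).

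**Step 1. Reproduce the plan's figures with no crossover.**

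Power = Φ{[|p₁ − p₂| − 1.96·√(2p̄(1 − p̄)/n)] / √[(p₁(1 − p₁) + p₂(1 − p₂))/n]}, where p̄ is the mean of the two risks.

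- Inpatient, 0.30 v 0.18, n = 265: (0.12 − 1.96 × 0.03710)/0.03673 = 1.287, power 0.901. The required size is 265 per arm, an exact match to N = 530.
- Outpatient, 0.12 v 0.06: 477 per arm are required, and 477/0.97 rounds up to 492, so N = 984 against the stated 1000. Power is 0.905 at 485 per arm and 0.913 at 500.

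The stated sizes are therefore what one obtains with no control use of the study drugs. The sample size paragraphs allow for loss to follow-up only.

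**Step 2. Dilute the control arm.**

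Control rate = p(1 − c·f·RRR). AZCT rate = p(1 − RRR). Expected ITT RRR = 1 − AZCT rate/control rate.

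Inpatient example, c = 20%, f = 1: control rate 0.30 × (1 − 0.2 × 0.4) = 0.276; ITT RRR 1 − 0.18/0.276 = 34.8%; power Φ[(0.096 − 1.96 × 0.03645)/0.03621] = Φ(0.678) = 0.751.

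| c | f | Inpatient control rate | ITT RRR | Power (265/arm) | Outpatient control rate | ITT RRR | Power (485/arm) |
|---|---|---|---|---|---|---|---|
| 0 | – | 30.0% | 40.0% | 0.901 | 12.0% | 50.0% | 0.905 |
| 5% | 0.5 | 29.7% | 39.4% | 0.887 | 11.85% | 49.4% | 0.893 |
| 10% | 0.5 | 29.4% | 38.8% | 0.872 | 11.7% | 48.7% | 0.879 |
| 20% | 0.5 | 28.8% | 37.5% | 0.838 | 11.4% | 47.4% | 0.848 |
| 30% | 0.5 | 28.2% | 36.2% | 0.797 | 11.1% | 45.9% | 0.812 |
| 5% | 1 | 29.4% | 38.8% | 0.872 | 11.7% | 48.7% | 0.879 |
| 10% | 1 | 28.8% | 37.5% | 0.838 | 11.4% | 47.4% | 0.848 |
| 20% | 1 | 27.6% | 34.8% | 0.751 | 10.8% | 44.4% | 0.770 |
| 30% | 1 | 26.4% | 31.8% | 0.644 | 10.2% | 41.2% | 0.670 |

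Only the product c·f enters, so 10% at half effect equals 5% at full effect.

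**Step 3. Cost of buying the power back with patients.** At full effect and c = 10%, 20% or 30%, keeping 90% power needs N = 642, 800 or 1026 inpatients, and 1142, 1400 or 1770 outpatients before the 3% loss. The diluted RRR would remain.

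**Step 4. What a restriction could recover.** Suppose it removes half or three quarters of a 20% crossover, leaving c = 10% or 5%. Both fractions are assumptions.

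| | f | Power at c = 20% | Half removed | Three quarters removed |
|---|---|---|---|---|
| Inpatient | 1 | 0.751 | 0.838 | 0.872 |
| Inpatient | 0.5 | 0.838 | 0.872 | 0.887 |
| Outpatient | 1 | 0.770 | 0.848 | 0.879 |
| Outpatient | 0.5 | 0.848 | 0.879 | 0.893 |

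**The case against.** - **This is a recognised pragmatic design.** An open-label comparison with unrestricted usual care, analysed by intention-to-treat, is valid as a treatment-policy contrast. That stands. The stated hypothesis, however, is about adding AZCT to usual care, and that question blurs if usual care contains AZCT.
- **The sentence may cover background therapy only.** AZCT is the named add-on, and the entry exclusion shows an intent to keep the contrast clean. This reading is possible, but no section says it, and the entry exclusion does not act after randomization.
- **The crossover rates are assumed.** This stands and limits the size of the claim. Section 1 mentions official recommendations of chloroquine, but for prophylaxis, so they make off-study use plausible without giving a rate. The same section's doubt about drug supply points the other way. For outpatients the relevant window closes at admission.
- **Existing provisions help.** Recording co-interventions lets crossover be described but does not prevent it. N is a minimum and may be raised (Synopsis, 3.3.3, 4.3.3). The reason given is uncertain progression rates, and a larger N restores power without undoing the attenuation.
- **The remedy is only advisory.** It will not remove all crossover, and azithromycin for other indications stays allowed. The recovery figures are therefore conditional.

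**Conclusion.** The concern holds. As written, both trials allow controls to receive the tested drugs for COVID-19 after randomization, and the primary analysis would absorb that use as dilution. The gap in the text is certain; its effect is not. Under an assumed 10% to 30% of controls treated before the event, power falls to between 87% and 64% for inpatients and between 88% and 67% for outpatients, depending on whether half or all of the effect is received. The expected RRR falls from 40% to between 38.8% and 31.8%, and from 50% to between 48.7% and 41.2%. At 5% with half effect the loss is trivial: power is 89% in both trials, or 90% for outpatients if all 500 per arm are evaluable. The sample size arithmetic is sound and intention-to-treat remains the right primary analysis. This should be fixed because the remedy is nearly free, although the protocol does not show that the harm will occur.

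**What to change.** In 3.4.2 and 4.4.2, continue the sentence on usual care with:

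*except that patients allocated to usual care should not be given chloroquine, hydroxychloroquine or azithromycin as treatment for COVID-19; use for a separate clinical indication is at the physician's discretion.*

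Leave all other care unrestricted and keep intention-to-treat as the primary analysis.

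The cost is one clause in each of two sections, with no new data, visits or analyses. Physicians lose a little freedom. Some dilution may remain from azithromycin given for other reasons: if that reached 10% of controls at half effect, power would still be 87% for inpatients and 88% for outpatients.
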